## I. Introduction

Essential tremor (ET) is a common progressive neurological disorder and is the most common movement disorder. Worldwide, up to 5% of the population suffer from this disorder with an increased incidence with advanced age (Agarwal and Biagioli 2018). Although essential tremor is considered as a benign disorder, studies have shown that quality of life in patients with ET is affected. Patients reported that the tremor interfered with their activities of daily living (Louis and Machado 2015), as well as, causing them anxiety and embarrassment (Chandran and Pal 2013).

The 2017 Movement society concusses statement includes the following criteria for the clinical diagnosis of essential tremor (Bhatia et al. 2018):

1. Isolated tremor syndrome of bilateral upper limb action tremor.
2. At least 3 years history of tremor.
3. With or without tremor in other locations (head, voice and lower limbs).
4. Absence of other neurological signs such as dystonia, ataxia and Parkinsonism.

The treatment possibilities currently available for patients with ET are scarce and were mostly discovered incidentally. The limitations of existing therapeutic options is partly attributable to the absence of an established clear-cut mechanism of ET seeing as neurotransmitter deficits, microscopic pathologies, and the genetic defects that cause ET have yet to be identified (Deuschl et al. 2011).

At present, patients with ET can be prescribed either pharmacological or non-pharmacological treatments. The options available have been approved for the treatment of ET; however it is important to note that many of the studies conducted to determine the efficacy of these remedies were based on small sample sizes and performed over a brief observation period (Schneider and Deuschl 2015).

1. **Pharmacological Treatment:** The medications available include Propranolol or Primidone as first line therapy as well as Benzodiazepines (Alprazolam), Topiramate or Gabapentin as second line treatments. The major downside to the available pharmacological remedies is that most of the patients may not tolerate the adverse events associated with these medications. Moreover, the available treatments have limited effectiveness and possess various contraindications that ultimately limit their use (Schneider and Deuschl 2015) (Hedera et al. 2013) (Zesiewicz et al. 2011).

2. **Non-pharmacological Treatment:** Surgical interventions are reserved for severe refractory cases of ET as they are rather invasive. Considering the predictable postoperative morbidity (Sadeghi and Ondo 2010) and major side effects experienced by patients limit their optimal use (Zesiewicz et al. 2013). These include Deep Brain Stimulation, Thalamotomy, Gamma Knife Thalamotomy and MRI-guided focused ultrasound. The adverse effects of these modalities may be unpredictable due to equipment malfunction and may include weakness, seizures, cognitive defects and others. (Zesiewicz et al. 2013)

The proposed mechanism that underlies ET, the central oscillating network, is mainly composed of the olivocerebellar system, thalamus and motor cortex (Raethjen and Deuschl 2012). The thalamocortical projections originates in the lower brainstem, passes through the thalamus and projects to the motor cortex. An interruption in the projections between the thalamus and the motor cortex limits the ability of the cortex to reorganize and restore ET (Chalah et al. 2015). In addition, unilateral subdural motor cortex stimulation was able to reduce contralateral hand tremor in two of the three studied patients with ET (Moro et al. 2011). Chalah et al described a case of 76 year old female with essential tremor that disappeared following a cortico-subcortical prerolandic stroke despite complete motor recovery (Chalah et al. 2015). These finding highlight the role of the motor cortex in ET production and possible therapeutic role of transcranial direct current stimulation.

Transcranial direct current stimulation (tDCS) has been used to treat a wide range of psychiatric and neurological disorders such as depression (Boggio et al. 2008), migraine (Antal et al. 2011), stroke (Schlaug et al. 2008) and Parkinson's disease (Benninger et al. 2010). tDCS is a type of non-invasive brain stimulation technique proven efficacious in modulating human cortical function by producing prolonged but reversible shifts in cortical excitability (Priori et al. 1998). This technique has the potential to be an ideal treatment option for essential tremor.

One of the most accepted effects of tDCS is its ability to modify neuronal membrane polarity depending on the polarity used (Nitsche and Paulus 2001). In other words, when the anode is placed over the motor cortical area, tDCS increases cortical excitability both during and following the stimulation. Whereas cathodal stimulation decreases cortical excitability. The

duration of tDCS effect depends on the duration and intensity of the stimulation (A. and W. 2000; Priori et al. 1998).

Most tDCS studies have adopted similar stimulation techniques. A pair of sponges (25-35cm^2) soaked in normal saline solution are placed over the stimulation site. The tDCS electrodes, made of metal or conductive rubber, are then wrapped in a perforated sponge pocket. Constant current of 1–2 mA is then delivered to the patient's scalp through anodal and cathodal electrodes with a ramp up and ramp down period of 30s at the start and end of the session (Zhao et al. 2017). Sham-controlled studies are easier with tDCS, because subjects rarely experience sensations related to the treatment. Ramping for 10 seconds at the beginning and end of tDCS, combined with a stimulation duration of 30 seconds in the sham condition, results in similar sensory experiences which make real tDCS and sham tDCS difficult to distinguish (Gandiga et al. 2006).

Importantly, tDCS has been shown to be safe in a number of trials (Brunoni et al. 2011). Worldwide, no major side effects have been reported in thousands of known human subjects (Nitsche et al. 2009). There is also individual data on patients who received over 100 sessions of tDCS for treatment of schizophrenia and depression that states that no adverse effects arose from cumulative exposure (Bikson et al. 2016). However, minor side effects such as sensation of itching under the electrodes, mild skin erythema and headaches have been reported but these are rarely disturbing and resolve after stimulation is halted (Brunoni et al. 2011).

Our primary goal is to evaluate the effects of cathodal tDCS of the motor cortex in essential tremor patients, particularly its effect on tremor amplitude, and quality of life. Should tDCS prove effective, this would be a breakthrough in the treatment of this condition, given its excellent safety profile, simplicity and affordability.

## **II. Study objectives**

### **Primary objectives**

The primary objective of the study is to assess the effect of cathodal tDCS stimulation of the motor cortex on tremor amplitude

### **Secondary objectives:**

The secondary objectives are to:

- Assess change from baseline tremor on clinical rating scale
- Assess change in quality of life

### **III. Study outcomes**

#### **Primary outcome:**

Change in tremor amplitude using an accelerometer pre and post cathodal tDCS of the motor cortex.

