#### **Secondary outcome:**

Measure change in baseline tremor and effect on quality of life using the TETRAS scale

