### **IV. Study methodology / design**

#### **Study design**

A randomized, sham-controlled, double blind and crossover study.

It will be carried at LAUMC-RH, Beirut, Lebanon over the course of 2 years.

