### **Study Population:**

The minimum sample size required for the study was obtained using the Chow et al. method. A difference of 30% in the accelerometer score will be considered significant. The minimal sample size needed per sequence is 17, so a total of 36 samples. In order to account for any possible dropout from the study we plan to enroll a total of 40 participants for the study. They will be randomly assigned to either one of the two arms (cathodal tDCS versus sham tDCS) as per study methodology discussed below.

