### **Post tDCS/Clinical evaluation**

Patient will be asked to fill out their TETRAS at days 1 and 5 of each tDCS session (cathodal and sham), and days 12 and 19 after each tDCS session (cathodal and sham). Please refer to figure 1.

Accelerometer assessment of the tremor will be performed at days 1 and 5 of each tDCS stimulation session (cathodal and sham).

**Figure 1:** Study design and procedure

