## **VI. Statistical Analysis**

The analysis will be conducted using the R statistical package. Demographic data will be summarized using frequencies, means, standard deviations and confidence intervals. The change in the TETRAS and Accelerometer scores will be assessed using Wilcoxon paired test at different time points (illustrated in figure 1) and the correlation between the TETRAS and Accelerometer scores will be tested using the Pearson method.

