## **XI. Dissemination of Results and Publication policy**

The data will be published in peer-reviewed journals. If the results show a significant improvement in essential tremor patients, further studies will be designed to study the optimal maintenance tDCS dose and the long term effect of tDCS.

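### The primary outcome is a before-and-after change around cathodal stimulation, and no section states the cathodal-versus-sham contrast that the sham-controlled crossover was built to estimate

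*Protocol*

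**What the plan says.** Section III (Primary outcome) reads: "Change in tremor amplitude using an accelerometer pre and post cathodal tDCS of the motor cortex". The primary objective in section II is likewise to "assess the effect of cathodal tDCS stimulation of the motor cortex on tremor amplitude", with no comparator. The secondary outcome is to "Measure change in baseline tremor and effect on quality of life using the TETRAS scale", again with no comparator.

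Section VI (Statistical Analysis) says: "The change in the TETRAS and Accelerometer scores will be assessed using Wilcoxon paired test at different time points (illustrated in figure 1". It names neither a treatment contrast nor the pairs to be compared.

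The design sections point elsewhere. Study design: "A randomized, sham-controlled, double blind and crossover study". Study Population: "A difference of 30% in the accelerometer score will be considered significant. The minimal sample size needed per sequence is 17". Post tDCS/Clinical evaluation: "Accelerometer assessment of the tremor will be performed at days 1 and 5 of each tDCS stimulation session (cathodal and sham". Amplitude is therefore collected at the same two times in both conditions.

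Section XI (Dissemination) looks ahead: "If the results show a significant improvement in essential tremor patients, further studies will be designed". Sham is not mentioned there either.

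**The concern.** The stated outcome and the design imply two different quantities. The outcome can be computed from the cathodal period alone. The crossover, the sham period and sizing by sequence serve only to estimate cathodal minus sham.

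A change within one condition mixes any effect of stimulation with placebo response, regression to the mean, familiarity with the test and drift over time. The sham period is there to remove these. If the primary result is reported as section III defines it, an improvement common to both conditions could be presented as efficacy and used to justify the further studies foreseen in section XI. Section VI admits either pairing, so the choice could also be made after the data are seen.

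**Working it through.** **1. Is the contrast stated anywhere?**

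| Protocol section | Wording concerns | Sham contrast stated? |
|---|---|---|
| II, primary objective | Effect of cathodal stimulation on amplitude | No |
| II and III, secondary objectives and outcome | Change on the rating scale and in quality of life | No |
| III, primary outcome | Change around cathodal stimulation | No |
| IV, Study design | Sham-controlled crossover | Implied only |
| IV, Study Population | 30% difference, size per sequence; cathodal set against sham only to label the arms | Implied only |
| V, Post tDCS | Accelerometry on days 1 and 5 in both conditions | Data available, contrast not stated |
| VI, analysis | Paired test over time points | No |

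**2. Does the sample size settle it?** For a 2x2 crossover, n per sequence = (z for alpha + z for power)² × SD² / (2 × delta²), where SD is that of the within-patient cathodal-minus-sham difference. The protocol gives delta = 0.30 and n = 17, but no SD, alpha, sidedness or power, so 17 cannot be reproduced. Solving for SD at two-sided 5% and 80% power: 0.30 × √34 / (1.960 + 0.842) = 0.62. At 90% power it is 0.54. Neither value is in the protocol, and nothing says whether the 30% is a change over time or a difference from sham. (2 × 17 is 34, not the stated 36; that is a separate point.)

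**3. What follows from using the stated outcome?** Assumptions, none from the protocol: normal change scores with SD 1 in each condition, no true cathodal-sham difference, the same improvement in both conditions, within-patient correlation 0.5, n = 36, two-sided 5% signed-rank tests, 20,000 simulated trials per setting.

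| Shared improvement (SD) | Cathodal before-and-after significant | Cathodal minus sham significant | Cathodal significant, sham not |
|---|---|---|---|
| 0 | 0.045 | 0.048 | 0.037 |
| 0.2 | 0.202 | 0.049 | 0.117 |
| 0.3 | 0.395 | 0.048 | 0.167 |
| 0.4 | 0.613 | 0.045 | 0.160 |
| 0.5 | 0.806 | 0.046 | 0.117 |

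A hand check by normal approximation, Φ(shift × √n − 1.96): at 0.2 SD, Φ(1.2 − 1.96) = 0.22; at 0.5 SD, Φ(3.0 − 1.96) = 0.85. The signed-rank values lie slightly below, as expected.

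For shifts of 0.2 and 0.5 SD, the before-and-after rejection rate is 0.190 and 0.786 with 34 patients, and 0.221 and 0.846 with 40. For shifts of 0.2 to 0.5 SD, the last column runs from 0.089 to 0.129 at correlation 0.7 and from 0.151 to 0.241 if the two changes are independent.

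**4. The same on the percentage scale.** Take the back-solved SD of 0.62 and independent changes, so that each condition's change has SD 0.62/√2 = 0.44. With n = 36 and shared improvements of 0, 10, 20 and 30%, the before-and-after test rejects in about 5, 25, 74 and 97% of trials. The contrast stays at 4 to 5%.

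**5. Which test of the contrast?** Assumed: 18 per sequence, correlation 0.5, a period shift of 0, 0.5 or 1.0 SD. Power is at a true difference of 0.5 SD.

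| Test | Type I error | Power |
|---|---|---|
| Plain paired Wilcoxon, cathodal minus sham | 0.047 / 0.029 / 0.005 | 0.811 / 0.726 / 0.483 |
| Rank-sum of period differences between sequences | 0.046 / 0.047 / 0.047 | 0.806 / 0.798 / 0.804 |

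Ignoring period does not inflate error here, but it costs power if a period effect exists.

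**The case against.** The strongest reply is that section III merely names the variable and leaves the comparison to the design. It does not exclude sham. Sizing per sequence makes sense only for a treatment comparison, Study Population sets cathodal against sham when naming the arms, and a paired test on change scores can naturally pair each patient's two changes. Figure 1, which section VI cites for the time points, is not visible here, and a separate analysis plan may fix the pairing. Section XI is a remark about future work, not a success criterion. The percentages rest on assumed shifts, and no section proposes the rule of declaring success when cathodal is significant and sham is not.

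Much of this is fair. The comparison with sham is very probably intended, section VI is ambiguous rather than plainly wrong, and the rates are illustrations. What the reply does not remove is the mismatch. The primary outcome belongs in the protocol, this protocol states one, and the one stated names only the cathodal condition. An analysis plan that tested cathodal minus sham would depart from the protocol's own definition. The figure is captioned as showing design and procedure and is cited only for timing. The wording about arms describes assignment, not a test.

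**Conclusion.** The concern holds. The primary outcome as worded does not use the randomised control, and no objective, outcome or analysis sentence supplies the missing contrast. This needs no numerical assumption: a change within one condition cannot be attributed to cathodal stimulation.

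The size does depend on assumptions. For 36 patients and a shared improvement of 0.2 to 0.5 SD, the stated outcome would be significant in about 20 to 81% of trials with no cathodal-sham difference, against about 5% for the contrast. Those are false positives only if the result is read as superiority over sham. With no shared improvement, both tests hold their 5% level. Because the point decides what the primary result means, it should be corrected before any data are analysed.

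**What to change.** - **Section III:** define the primary outcome as the within-patient difference, cathodal minus sham, in the day 1 to day 5 change in accelerometer amplitude. Say which of the two recorded positions (rest or postural) it uses.
- **Section VI:** state that the primary test is of this difference, with a method that allows for period, such as a rank-sum comparison of within-patient period differences between the two sequences, or a mixed model with treatment, period and sequence. Keep the before-and-after tests within each condition as descriptive.
- **Section IV, Study Population:** state that the 30% difference refers to this contrast.
- **TETRAS:** apply the same contrast at day 5 and at the two follow-up ratings (days 12 and 19).
- If figure 1 or an analysis plan already fixes the contrast, bring section III into line with it.

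The cost is a few sentences and a little more analysis work. No patients, visits or measurements are added, because both conditions are already measured on days 1 and 5.

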#### **Secondary outcome:**

Measure change in baseline tremor and effect on quality of life using the TETRAS scale

### **IV. Study methodology / design**

#### **Study design**

A randomized, sham-controlled, double blind and crossover study.

It will be carried at LAUMC-RH, Beirut, Lebanon over the course of 2 years.

#### **Study setting**

Lebanese American University Medical Center Risk Hospital (LAUMC-RH), Beirut, Lebanon

#### **Participants**

We will recruit 40 Patients diagnosed with essential tremor based on the 2017 movement society criteria (Bhatia et al. 2018)

Inclusion Criteria	Exclusion Criteria

• Patients who fulfil the 2017 Movement society concusses statement criteria for essential tremor

• Age 18 and above

	

• Isolated focal tremor (voice, head)

• Orthostatic tremor with a frequency of more than 12 Hz

• Task and position specific tremor

• Sudden onset and stepwise deterioration of tremor

• History of substance abuse or dependence in the past

	
 
• Comorbid medical conditions and medications capable of producing or enhancing tremors
 
• History of neurological disorders, brain tumors, brain surgery or abnormal neurological examination
 
• Epileptic disorders
 
• Cardiac pacemakers
 
• Metallic hardware in the head or scalp (surgical clips)
 
• Eczema or skin abrasion at the intended site of stimulation
 
• Currently pregnant or plan for pregnancy in the next 6 months
 
• Patients with prior experience with tDCS
 
• Major psychosocial problems or medical problems rendering informed consent impossible
 

--	---

### **Study Population:**

The minimum sample size required for the study was obtained using the Chow et al. method. A difference of 30% in the accelerometer score will be considered significant. The minimal sample size needed per sequence is 17, so a total of 36 samples. In order to account for any possible dropout from the study we plan to enroll a total of 40 participants for the study. They will be randomly assigned to either one of the two arms (cathodal tDCS versus sham tDCS) as per study methodology discussed below.

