### **Recruitment and randomization**

Patients who had visited or will visit LAUMC-RH with a diagnosis of ET on their records would be contacted and those interested in participating in the trial would be randomly assigned into either (1) cathodal tDCS or (2) sham tDCS.

One researcher who will not be blinded to group assignment will perform cathodal tDCS or sham tDCS. However, another researcher who will assess the outcome measures will be blinded to group assignment. The third blinded researcher will collect the demographic data

and assess adverse events. All participants will be blinded to the order in which the cathodal/sham conditions will be given.

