### tDCS sessions:

Prior to starting the first tDCS session, the patient will be asked to fill his/her first TRG essential tremor assessment (TETRAS) scale which includes an activity of daily living subscale and a performance subscale (Elble et al. 2012).

The physician will then quantitatively analyze the tremor on the most affected side using an accelerometer. Two measures are obtained with the accelerometer: the tremor frequency and amplitude. Sensors are fixed on the skin at a given landmark (index finger) (Grimaldi and Manto 2010). The tremor will be assessed in two different positions: (1) at rest and (2) postural.

Subsequently TMS of the motor cortex contralateral to the hand used above will be performed with a figure-of-eight coil (70 mm) on a Magstim machine. To determine the optimal site of stimulation (hotspot), the coil will be moved around the primary motor cortex (M1) eliciting the largest MEP motor-evoked potentials (MEPs) from the first dorsal interosseous (FDI) of the hand tested above.

[figure not shown]
Finally, cathodal tDCS will be administered through a pair of conductive rubber electrodes covered by saline soaked sponges (35 cm^2). The current will be delivered continuously at 2 mA for 30 min through a battery-driven constant-current stimulator. The cathode will be positioned on the area representing the primary motor cortex and the anode over the contralateral supraorbital area.

tDCS stimulation (cathodal and sham) will be done daily for 5 consecutive days during weeks 1 and 5. Each stimulation session will last 30 minutes. tDCS will be performed while the patient is at rest, without any concurrent cognitive or motor task. The two tDCS sessions will be separated by a 23 day washout period.

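### The per-sequence and total sample sizes disagree: two sequences of 17 make 34, while a total of 36 needs 18 per sequence

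*Protocol*

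**What the plan says.** The Study Population section names a cited method, sets a 30% difference in the accelerometer score as the difference of interest, and reports the result: "The minimal sample size needed per sequence is 17, so a total of 36 samples". It then adds a margin for attrition: "In order to account for any possible dropout from the study we plan to enroll a total of 40 participants". The Participants section repeats that enrolment figure: "We will recruit 40 Patients diagnosed with essential tremor based on the 2017 movement society criteria".

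Four places fix the number of sequences:

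- Study design: "A randomized, sham-controlled, double blind and crossover study".
- tDCS sessions: "tDCS stimulation (cathodal and sham) will be done daily for 5 consecutive days during weeks 1 and 5".
- Recruitment and randomization: "All participants will be blinded to the order in which the cathodal/sham conditions will be given".
- Study Population: "They will be randomly assigned to either one of the two arms (cathodal tDCS versus sham tDCS".

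The protocol gives no significance level, power, standard deviation or expected dropout rate.

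**The concern.** The sentence presents the total as following from the per-sequence number, but in a two-sequence design it does not. These two figures are the only stated result of the sample size calculation, and they differ by one patient per sequence.

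At stake is which requirement the trial was planned to meet, and therefore how much dropout the 40 enrolled patients can absorb. Because no dropout rate is stated, a reader can judge that margin only from the required total, and the required total is the figure in doubt.

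**Working it through.** **Inputs from the protocol**

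- Patients per sequence: 17 (Study Population).
- Total before dropout: 36 (Study Population).
- Planned enrolment: 40 (Study Population and Participants).
- Number of sequences: 2. Each patient receives both conditions, one in week 1 and the other in week 5, so the possible orders are cathodal then sham, or sham then cathodal. Study Population also speaks of two arms.

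**Attempt to reproduce the stated total**

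Total = number of sequences × patients per sequence = 2 × 17 = 34. The stated 36 is not reproduced. Working backwards, 36 / 2 = 18 per sequence, and 36 / 17 = 2.12, which is not a whole number of sequences.

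**Other readings tried**

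- *Dropout already included in 36.* The protocol adds dropout in the next sentence, in the step to 40.
- *The total counts patient-periods.* 34 patients × 2 periods = 68, not 36.
- *Rounding up to balance the sequences.* 34 is already even and splits equally. No rounding or block-size step is described.
- *A third sequence or unequal allocation.* The protocol mentions neither.

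**Can the protocol show which figure is the slip?**

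The usual formula for testing equality in a two-sequence crossover is n per sequence = (z_α/2 + z_β)² × SD² / (2 × δ²), where SD is the standard deviation of the within-patient difference. Solving for SD gives SD = δ × √(2n) / (z_α/2 + z_β). I take δ = 0.30 from the protocol and assume a two-sided 5% level, which the protocol does not state:

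| Assumed power | SD implied by n = 17 | SD implied by n = 18 |
|---|---|---|
| 80% | 0.30 × √34 / 2.80 = 0.62 | 0.30 × √36 / 2.80 = 0.64 |
| 90% | 0.30 × √34 / 3.24 = 0.54 | 0.30 × √36 / 3.24 = 0.56 |

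The implied standard deviations are nearly the same, and the protocol gives none to compare them with. The slip cannot be located from the document.

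**Size of the discrepancy**

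- Dropout room if 34 are needed: (40 − 34) / 40 = 6 / 40 = 15%.
- Dropout room if 36 are needed: (40 − 36) / 40 = 4 / 40 = 10%.
- Detectable difference, with variability, level and power held fixed (normal approximation): √(36 / 34) = 1.029, so about 3% larger with 34 patients than with 36.
- Power, under an assumed two-sided 5% level (normal approximation): a trial with 80% power at 36 has 77.7% at 34, and one with 80% at 34 has 82.2% at 36. Starting from 90%, the figures are 88.3% and 91.6%. The change is about 2 percentage points.

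**The case against.** The strongest objection concerns weight. The number that governs recruitment is 40, which is stated consistently and exceeds both totals. No interim analysis is planned, and no rule in the protocol uses 34 or 36. The power figures compare trials with exactly 34 and 36 completers, whereas the number analysed will depend on actual dropout from 40. They also rest on an assumed level and power and on a normal approximation, while the Statistical Analysis section plans a paired Wilcoxon test. These points stand: the power figures only illustrate the size of the gap and do not show harm to the trial.

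A second objection is that 36 may be the sound figure. An unrounded requirement between 17.5 and 18 per sequence, doubled and then rounded up, gives 36; truncating the same value would give 17. That is possible, although the protocol does not say it. It would move the error to the per-sequence figure without removing it, since the stated minimum per sequence should then be 18.

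Third, room for 15% or for 10% dropout contradicts nothing, because no dropout rate is stated. This is also correct: the two margins are a consequence of the discrepancy and do not form a second inconsistency.

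None of these objections makes 17 per sequence and 36 in total true together.

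**Conclusion.** The concern holds. With two sequences, 17 per sequence gives 34 and a total of 36 needs 18, so one of the two stated figures is wrong. The discrepancy is 2 patients in total. This conclusion rests only on the two-sequence design that the protocol describes and on equal allocation, from which the protocol gives no departure.

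The consequence is minor. It does not show that the trial is underpowered, and it does not call the 40 enrolled patients into question. It should still be corrected, because a stated sample size is a figure that readers rely on and only the sponsor holds the inputs needed to settle it.

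**What to change.** Check the original calculation and amend the one sentence in Study Population to whichever of these it supports:

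- 17 per sequence and 34 in total, so that 40 enrolled allows for 6 dropouts (15%); or
- 18 per sequence and 36 in total, so that 40 enrolled allows for 4 dropouts (10%).

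Stating the resulting dropout allowance in the same place would make the step to 40 traceable. The cost is one corrected sentence; enrolment stays at 40.
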